COMIRB Protocol

COLORADO MULTIPLE INSTITUTIONAL REVIEW BOARD
[name] [contact] [contact]

Protocol #: 16-1785

Project Title: Evaluation of Moderate to Severe Influenza Disease in Children 6 months to 8 years in Colorado

Principal Investigator: [name]

Version Date: 7/27/16

I. Hypotheses and Specific Aims:

Children 6 months to 8 years of age with moderate to severe influenza have a higher risk of hospitalization, intensive care unit (ICU) admission, antibiotic use and complications compared with children with mild influenza illness.

Specific Aims:

Aim #1: To determine the validity of the moderate to severe endpoint for influenza as a predictor for hospitalization among children aged 6 months to 8 years evaluated at Children's Hospital Colorado (CHCO) emergency department (ED) and urgent cares (UC) during the 2016-2017 influenza season.

Aim #2: To prospectively evaluate the usefulness of the moderate to severe influenza endpoint against additional severity measures such as ICU admission, antibiotic and antiviral use, parental and child absenteeism and recurrent healthcare visits among children aged 6 months to 8 years evaluated at ED and UC centers in Colorado.

Aim # 3: To compare the healthcare costs associated with management of moderate to severe versus mild influenza disease.

Exploratory Objectives:

- 1) To compare the moderate to severe influenza definition, and other severity measures such as ICU admission, hospitalization, antibiotic, antiviral use, child and caregiver absenteeism among patients vaccinated with injectable influenza vaccine (IIV) versus unvaccinated individuals.
- 2) To evaluate severity measures such as hospitalization, ICU admission, antibiotic, antiviral use, caregiver and child absenteeism among children with influenza like illness who test negative for influenza.
- 3) To determine whether clinical measurements taken at ED/UC presentation such as systemic inflammatory response syndrome (SIRS) criteria, adjusted heart rate, oxygen saturation and temperature predict hospitalization, ICU admission and having polymerase chain reaction (PCR)-confirmed influenza. We will also consider the prediction value of peak temperature and temperature duration.

II. Background and Significance:

Influenza is an important cause of morbidity in children, annually causing 1-7 hospitalizations per 10,000 in US children under the age of 18 years (1-6). Children are

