The purpose of the proposed study is to validate that the definition of moderate to severe influenza in children predicts greater risk of healthcare endpoints such as hospitalization, increased length of stay, use of antimicrobials (including antivirals), absenteeism, increased duration of illness, and increased healthcare costs.

Understanding and validating the relationship between moderate to severe influenza and these clinically relevant endpoints is critical to establishing relevant surrogate markers of clinical and public health outcomes. If shown to be clinically relevant, this definition of moderate to severe influenza can be an important endpoint for assessing influenza vaccine effectiveness.

III. Preliminary Studies/Progress Report:

CHCO provides an ideal site for the study of influenza in children. CHCO is a large tertiary institution with a large catchment area of Denver Metro, Aurora and surrounding states. It serves 67% of children in the state of Colorado. From December 1, 2010 to April 30, 2014, there were 409 patients admitted to CHCO with PCR-confirmed influenza; 62% of these were defined as high-risk (16), and 38% were vaccinated against influenza during the same season. Accurate immunization data was available for 83% of patients via the Colorado Immunization Information System (CIIS). Clinical presentation and

hospital-based outcomes such as length of hospitalization among children admitted with influenza are shown in Table 1.

Table 1. Children Admitted To CHCO with Influenza, 2010-2014

Children admitted to CHCO with influenza N = 395	< 3 years N = 156	>3 years N = 239
Otitis media	10 (6)	6 (3)
Pneumonia	7 (5)	22 (9)
Hypoxia	19 (12)	141 (59)
Fever	133 (85)	207 (87)
Median duration of fever, days (range)	2 (1-17)	4 (1-64)
Tachypnea	64 (41)	91 (38)
Antibiotics	88 (56)	157 (66)
Median duration of antibiotics, days (range)	7 (0-23)	8 (0-77)
Pediatric Intensive Care Unit (PICU)	55 (35)	81 (34)
PICU length of stay, days	2 (1-100)	3(1-83)
Death	1 (1)	2 (1)
Median duration of hospitalization, days (range)	3 (1-100)	3 (1-128)
Vaccinated during current season against influenza	39 (25)	87 (36)

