- 6) Number of days of absenteeism from work in caregivers of children presenting to the CHCO Main ED or North Campus UC with influenza
- 7) Healthcare costs associated with ED visits or hospitalization in patients presenting to the CHCO Main ED or North Campus UC with influenza

Exploratory Outcome measures/Endpoints:

1) Vaccination status in subjects testing positive for influenza:

- a. Injectable influenza vaccine (IIV) receipt in patients presenting to the CHCO Main ED or North Campus UC with moderate to severe influenza
- b. IIV receipt in patients presenting to the CHCO Main ED or North Campus UC who are hospitalized
- c. IIV receipt in patients presenting to the CHCO Main ED or North Campus UC who are admitted to the ICU
- d. Number of days of fever in patients who received IIV presenting to the CHCO Main ED or North Campus UC
- e. Number of days of caregiver and child absenteeism in patients who received IIV presenting to the CHCO Main ED or North Campus UC

- f. IIV receipt in patients presenting to the CHCO Main ED or North Campus UC who received antibiotics
- g. IIV receipt in patients presenting to the CHCO Main ED or North Campus UC who received antivirals

2) Influenza-like-illness among subjects testing negative for influenza:

- a. Hospitalization in patients with ILI who test negative for influenza
- b. ICU admission in patients with ILI who test negative for influenza
- c. Duration of fever in patients with ILI who test negative for influenza
- d. Number of days of absenteeism from work in caregivers of patients with ILI who test negative for influenza
- e. Number of days of absenteeism from school in patients with ILI who test negative for influenza
- f. Antibiotic use in patients with ILI who test negative for influenza
- g. Antiviral use in patients with ILI who test negative for influenza

3) Fever, vital sign data and extrapulmonary complications:

- a. Number of days of fever in patients presenting to the CHCO Main ED or North Campus UC with influenza
- b. Peak temperature at any time during illness in patients presenting to the CHCO Main ED or North Campus UC with influenza
- c. Modified SIRS criteria met in patients presenting to the CHCO Main ED or North Campus UC with influenza
- d. Initial and peak adjusted heart rate in patients presenting to the CHCO Main ED or North Campus UC with influenza
- e. Oxygen saturation in patients presenting to the CHCO Main ED or North Campus UC with influenza

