For all study objectives, we will present data descriptively using frequencies for categorical variables and measures of central tendency for continuous variables. We will explore bivariable associations between moderate to severe versus mild influenza for covariates including demographic factors and clinical factors outlined above. Proportions will be compared using Chi-square test. Mean values will be compared using student's t test for normally-distributed data, otherwise Wilcoxon-Rank-Sum test will be used.

Aim #1/Primary Endpoint Analysis: We will use logistic regression to estimate odds ratios (and 95%CI) for hospitalization, adjusted for significant covariates at the level of $P < 0.2$ on bivariable analysis; and other covariates selected *a priori* that could affect outcomes such as hospitalization (age group, high risk medical condition, vaccination status, influenza type). We will verify to ensure statistical assumptions are met for each model. The intraclass correlation coefficient will be estimated and a multi-level model will be used if we need to account for multiple visits per child. If we use a multi-level model, the optimal covariance structure will be determined through the examination of information criteria statistics and graphical techniques.

Aim #2/Secondary Endpoint #1-6 Analysis: We will use logistic regression to estimate each of our dichotomous secondary outcomes of interest, ICU admission, antibiotic,

antiviral use, adjusted for significant covariates at the level of $P < 0.2$ on bivariable analysis; and other covariates selected *a priori* that could affect outcomes such as hospitalization (age group, high risk medical condition, vaccination status, influenza type). We will verify to ensure statistical assumptions are met for each model. The intraclass correlation coefficient will be estimated and a multi-level model will be used if we need to account for multiple visits per child. If we use a multi-level model, the optimal covariance structure will be determined through the examination of information criteria and graphical techniques. We will also explore our secondary outcomes of interest expressed as continuous variables (number of recurrent visits to the ED, duration of absenteeism in days). We will use a log linear model to compare these variables between the mild versus moderate to severe influenza groups and will exponentiate the coefficients to yield geometric mean ratios.

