Aim #3/Secondary Endpoint #7 Analysis: An economic analysis will be conducted to compare the healthcare costs in the mild and moderate to severe influenza groups. We will work with the finance department at CHCO to obtain charge data for each influenza-related ED visit and hospitalization. Direct costs associated with healthcare utilization will be obtained by collecting hospital charge data and applying a cost to charge ratio to estimate costs. Mean costs and standard deviations for each group will be determined and compared using t tests for normally distributed data, and presented as median (IQR) costs with analysis conducted using non parametric tests for non-normally distributed data. Relative healthcare costs will be modeled on log-transformed data using linear regression or a generalized linear model, depending on the data distribution.

Exploratory Objective #1-2/Exploratory Endpoints #1-2: In addition to the primary and secondary outcomes outlined above, we will also assess the odds ratios and 95% CI of several exploratory dichotomous outcomes –moderate to severe influenza, hospitalization, ICU admission, antibiotics and antiviral use among patients with IIV versus unvaccinated children using log linear regression in a manner similar to the above specific aims. For continuous variables (duration of fever, number of days of absenteeism), we will use a log linear model as described for our prior secondary outcomes.
We will conduct a similar analysis as outlined above for patients with influenza like illness who test negative for influenza using the clinical severity outcome measures outlined.

Exploratory Objective #3/Exploratory Endpoint#3: We will determine the predictive value for hospitalization, ICU admission and having PCR-confirmed influenza of duration of fever, SIRS criteria, adjusted heart rate, respiratory rate and oxygen saturation using logistic regression models with two-way interactions between factors in the model when needed. We will use the Brier score to assess overall model performance and the c statistic to assess discriminative ability. In addition to logistic regression, we will explore machine learning methods for the predictive modeling of these three outcomes. The predictive value of peak temperature will also be assessed using a logistic regression model.

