Using these sample size estimates (using sample size of 408), assuming 50% vaccination status, and a ratio of IIV to LAIV receipt among vaccinated individuals of 9:1, we will have 80% power at a 0.05 significance level to detect an odds ratio of 3 for hospitalization among the mild versus moderate to severe cases, among patients vaccinated with IIV. We won't be adequately powered to detect a statistically significant difference for LAIV recipients.

Figure 1. Flowchart to produce the analysis sample*

*N's are conservative estimates based on data from Children's Hospital Colorado collected during the 2014-2015 flu season

**Primary outcome of interest

G. Summarize Knowledge to be Gained:

Influenza is an important public health and clinical challenge, and contributes to a significant burden of disease among children. Understanding and validating the relationship between moderate to severe influenza and clinically relevant endpoints such as ED visits, hospitalizations and ICU admissions is critical to establishing relevant surrogate markers of clinical and public health outcomes. If shown to be clinically relevant, this definition of moderate to severe influenza can be an important endpoint for assessing influenza vaccine effectiveness.

H. References:

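### Does the power statement for injectable-vaccine (IIV) recipients need replacing because it describes a contrast that the analysis plan does not contain?

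*Combined protocol and SAP*

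**What the plan says.** Under Power and sample size calculations (Section IV.F), the plan needs 408 influenza-positive children, 30% mild and 70% moderate to severe, for 80% power at the 0.05 level to detect an odds ratio of about 2 for hospitalization. With the same assumptions, 151 children suffice for an odds ratio of 3. The plan then takes the 408, "assuming 50% vaccination status, and a ratio of IIV to LAIV receipt among vaccinated individuals of 9:1", and claims 80% power "to detect an odds ratio of 3 for hospitalization among the mild versus moderate to severe cases, among patients vaccinated with IIV". It adds that the LAIV group is too small for a comparison.

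The vaccine analyses are described differently elsewhere:

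- Section I, exploratory objective 1, compares severity measures "among patients vaccinated with injectable influenza vaccine (IIV) versus unvaccinated individuals".
- Section IV.A, exploratory endpoint 1a, is "Injectable influenza vaccine (IIV) receipt in patients presenting to the CHCO Main ED or North Campus UC with moderate to severe influenza". The other endpoints under that heading are IIV receipt by outcome, or durations in IIV recipients.
- Section IV.F, Exploratory Objective #1-2, estimates odds ratios for several dichotomous outcomes, one of which is moderate to severe influenza itself. The list ends with "antibiotics and antiviral use among patients with IIV versus unvaccinated children", which fixes the two groups to be compared.
- In the Aim 1 and Aim 2 models, vaccination is one of the covariates chosen in advance ("age group, high risk medical condition, vaccination status, influenza type").

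**The concern.** The power sentence and the analysis plan answer different questions. In the power sentence severity is the exposure, hospitalization is the outcome, and the analysis is confined to IIV recipients. In the planned vaccine analysis IIV receipt is the exposure, and moderate to severe influenza is one of the outcomes. The Aim 1 and 2 models contain no severity-by-vaccination interaction and no fit restricted to IIV recipients, and neither sensitivity analysis is by vaccination status.

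So the only quantified power statement about vaccination belongs to a contrast nobody has planned, and the planned contrast has none. A reader of the vaccine results might take an odds ratio of 3 as the smallest effect the study could detect. The power text also gives no hospitalization rate, no covariate R² and no sidedness, so the 80% cannot be rederived from that text alone. If the 80% were wrong, or if the missing statement left the vaccine analysis undefined, the plan would need correcting.

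**Working it through.** **Inputs from the plan.** N = 408; 30/70 severity split; 80% power; level 0.05; odds ratios 2 and 3; 50% vaccinated; IIV:LAIV 9:1.

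**Assumed inputs.** The test is two-sided, in keeping with the planned 95% confidence intervals. Table 2 supplies stand-in hospitalization rates: 486/1688 = 28.8% (2014-2015) and 940/2932 = 32.1% (both seasons). These cover all acute respiratory illness, partly at other sites, and the admission row is not said to share its denominator's restrictions. R² is taken as 0 to 0.1.

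**1. The plan's own figures.** With p0 and p1 the rates in mild and moderate to severe cases, B = 0.7 and P = 0.3·p0 + 0.7·p1,

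n = [1.96·√(P(1−P)/B) + 0.84·√(p0(1−p0) + p1(1−p1)(1−B)/B)]² / [(p1−p0)²(1−B)(1−R²)].

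Setting P = 32.1% with an odds ratio of 2 gives p0 = 22.2% and p1 = 36.3%. Then n = 392 at R² = 0, and 408 at R² = 0.04. Keeping p0 and R² and using an odds ratio of 3 (p1 = 46.1%) gives n = 153, against the stated 151. Other pairs fit about as well: p0 = 22.6% with R² = 0.05 gives 408 and 153; p0 = 25% with R² = 0.10 gives 408 and 155. The two stated sizes are compatible with each other and with a rate close to Table 2. They do not identify one set of inputs.

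**2. The IIV sentence.** IIV recipients: 408 × 0.5 × 0.9 = 183.6, about 184, which exceeds 151. Power for an odds ratio of 3 with 184 children, split 30/70, is 87% under each of the three input pairs in step 1. The stated 80% is conservative.

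It does depend on the 50% uptake. Section III reports that among children admitted with influenza in 2010-2014 "38% were vaccinated against influenza during the same season". If that applied to the enrolled children, there would be 408 × 0.38 × 0.9 = 140 IIV recipients and power would be about 76%.

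**3. The planned comparison.** Unvaccinated: 408 × 0.5 = 204. Detectable odds ratio, IIV versus unvaccinated, 184 against 204, 80% power, two-sided 0.05, pooled two-proportion formula with both group sizes multiplied by (1 − R²):

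| Outcome and assumed rate in the unvaccinated | R² = 0 | R² = 0.1 |
|---|---|---|
| Hospitalization, 28.8% | 0.50 | 0.48 |
| Hospitalization, 32.1% | 0.52 | 0.50 |
| Moderate to severe influenza, 70% | 0.55 | 0.54 |

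If 28.8% and 32.1% are read as the rate over both groups combined, the values at R² = 0 are 0.53 and 0.54. With 38% uptake (140 against 408 × 0.62 = 253), and the rates again read as those in the unvaccinated, they are 0.48 and 0.50.

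The answer changes if hospitalization is much rarer. At 11.5% (1375 admissions over 11,997 visits, all ages and including clinics) the detectable odds ratio is 0.31 if that is the rate in the unvaccinated and 0.39 if it is the overall rate.

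**4. What the sentence controls.** The target of 408, and the 408/0.25 = 1632 children to be tested, come from the primary aim. The vaccine odds ratios and their intervals come from the Exploratory Objective #1-2 text. Neither uses the IIV power sentence.

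**The case for a change.** The strongest case for a change is that the mismatch needs no assumption to establish, sits in the only quantified vaccine power statement, and would cost one sentence to mend. A reader could carry the figure of 3 over to a comparison that, at Table 2 rates, is sensitive to about a two-fold difference in odds. Stating the rate, R² and sidedness would also let the primary 80% be checked.

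The textual part stands. One could read exploratory objective 1 as asking how the severity definition performs by vaccination status, which would make the power sentence relevant, but the analysis text lists moderate to severe influenza as an outcome, so that reading is weak.

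The consequence does not stand. The sentence names its own contrast, so a careful reader will not transfer it. A reader who did would, at those rates, underrate the vaccine comparison and claim nothing extra for it. The plan promises no power for its exploratory objectives, and objectives 2 and 3 have none either.

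On the inputs, the text does give N, the severity split, level, power and odds ratios. The sample flowchart is not reproduced in the copy reviewed and may hold the hospitalization rate, so that rate cannot be called absent. R² and sidedness would be useful documentation, but their omission does not show the 80% to be wrong. A replacement sentence would itself need an assumed hospitalization rate, for which Table 2 is only a rough guide.

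**Conclusion.** This is a minor reporting inconsistency, and no change to the plan follows. The power sentence describes severity within IIV recipients, while the planned vaccine analysis is IIV versus unvaccinated. Under the plan's assumptions the stated 80% is met with room to spare (184 children against 151 needed, about 87% power), and the planned comparison can detect an odds ratio of about 0.5 at assumed hospitalization rates of 29% to 32%. Both statements rest on two-sided testing, 50% uptake with a 9:1 IIV:LAIV split, and Table 2 as a stand-in for the hospitalization rate. At 38% uptake the within-IIV power is about 76%; at much lower hospitalization rates the vaccine comparison is clearly less sensitive. Neither case affects the primary aim or the validity of the exploratory odds ratios, whose 95% intervals will show the precision actually reached. An analyst following the plan as written would run the same models and report the same results whether or not the sentence were reworded.
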